### **7.1. Discontinuation of Study Intervention**

Discontinuation of study treatment does not represent withdrawal from the study.

Participants may discontinue study treatment at any time for any reason or be discontinued from the study treatment at the discretion of the investigator should any untoward effect occur. In addition, a subject may be withdrawn by the investigator or the sponsor if enrollment into the trial is inappropriate, the trial plan is violated or for administrative and/or other safety reasons.

A subject must be discontinued from the trial for the following reasons:

- the participant or the participant's designee, for example, parents or legal guardian requests to discontinue investigational product.
- the subject is lost to follow -up

A subject must be discontinued from trial treatment but continue to be followed for any of the following reasons:

- the patient becomes pregnant during the study
- the patient is significantly noncompliant with study procedures and/or treatment
- disease progression. Disease progression should be confirmed per iRECIST 4 to 8 weeks after site-assessed first radiologic evidence of PD in clinically stable participants. Participants, who have unconfirmed disease progression may continue on treatment at the discretion of the investigator until progression per iRECIST. Any participant deemed clinically unstable should be discontinued from study treatment at first radiologic evidence of PD and is not required to have repeat tumor imaging for confirmation of PD by iRECIST.
- unacceptable toxicity
- the patient, for any reason, requires treatment with another therapeutic agent that has been demonstrated to be effective for treatment of the study indication. Discontinuation from study invention will occur prior to introduction of the new agent.
- Recurrent Grade 2 pneumonitis
- Discontinuation of treatment may be considered for participants who have attained a confirmed complete response (CR) and have been treated for at least 8 cycles (at least 24 weeks), receiving [for monotherapy: at least 2 doses of pembrolizumab; for

combination treatment: 2 cycles of the combination including 2 doses of pembrolizumab and at least 75% of the planned doses of LY3475070] beyond the date when the initial CR was declared.

- Pembrolizumab will be discontinued after completion of approximately 2 years of treatment with pembrolizumab (completion of 35 treatments with pembrolizumab).  
Note: The number of treatments is calculated starting with the first dose of pembrolizumab.

Participants discontinuing from the investigational product prematurely for any reason should complete adverse event and other follow-up procedures per Section 1.3 (Schedule of Activities), Section 8.3 (Adverse Events and Serious Adverse Events), and Section 8.2 (Safety Assessments) of the protocol.

## **7.2. Participant Discontinuation/Withdrawal from the Study**

Participants will be discontinued in the following circumstances:

- enrollment in any other clinical study involving an investigational product or enrollment in any other type of medical research judged not to be scientifically or medically compatible with this study
- participation in the study needs to be stopped for medical, safety, regulatory, or other reasons consistent with applicable laws, regulations, and good clinical practice (GCP)
- subject decision
  - the participant or the patient's designee, for example, parents or legal guardian requests to be withdrawn from the study
- the patient becomes pregnant during the study. See Section 8.3 regarding regulatory reporting requirements on fetal outcome.
- Participants discontinuing from the study prematurely for any reason should complete AE and other safety follow-up per Section 1.3 (Schedule of Activities), Section 8.3 (Adverse Events and Serious Adverse Events), and Section 8.2 (Safety Assessments) of this protocol.

### **7.2.1. Discontinuation of Inadvertently Enrolled Patients**

If the sponsor or investigator identify a participant who did not meet enrollment criteria and was inadvertently enrolled, then the patient should be discontinued from study treatment unless there are extenuating circumstances that make it medically necessary for the patient to continue on study treatment. If the investigator and the sponsor CRP agree it is medically appropriate to continue, the investigator must obtain documented approval from the sponsor CRP to allow the inadvertently enrolled participant to continue in the study with or without treatment with investigational product. Safety follow up is as outlined in Section 1.3 (Schedule of Activities), Section 8.3 (Adverse Events and Serious Adverse Events), and Section 8.2 (Safety Assessments) of the protocol.

Please refer to Appendix 7 for discontinuation of inadvertently enrolled patients in the United Kingdom.

### **7.3. Lost to Follow up**

A participant will be considered lost to follow-up if he or she repeatedly fails to return for scheduled visits and is unable to be contacted by the study site. Site personnel are expected to make diligent attempts to contact participants who fail to return for a scheduled visit or were otherwise unable to be followed up by the site.

Site personnel, or an independent third party, will attempt to collect the vital status of the participant within legal and ethical boundaries for all participants randomized, including those who did not get investigational product. Public sources may be searched for vital status information. If vital status is determined, this will be documented and the participant will not be considered lost to follow-up.

Lilly personnel will not be involved in any attempts to collect vital status information.

Discontinuation of specific sites or of the study as a whole are handled as part of Section 10.1.7.

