**Overall Design:**

Study JZMA is an open-label, multi-center, Phase 1 study of LY3475070, a CD73 inhibitor, alone or in combination with pembrolizumab in patients with advanced solid tumors.

In **Cohort A** of Phase 1a, single agent LY3475070 will be evaluated in at least 3 evaluable patients per dose level (DL). Dose escalation will be guided by the modified toxicity probability interval 2 (mTPI-2) method. It is anticipated that 4 dose levels will be evaluated to determine the recommended phase 1b dose of single agent LY3475070. Once the dose level DL2 (300 mg once a day [QD]) for single agent LY3475070 has been determined safe and tolerable, LY3475070 in combination with pembrolizumab is planned to be evaluated at 3 dose levels in **Cohort B**, starting at combination dose level 1 (150 mg QD).

Phase 1b of the study aims to confirm the recommended phase 2 dose (RP2D) for LY3475070 monotherapy and LY3475070 in combination with pembrolizumab, and to further evaluate safety and preliminary efficacy in 3 patient cohorts:

- **Cohort C** will consist of patients with programmed cell death protein-1/ligand 1 (PD-1/L1) refractory non-small cell lung cancer, renal cell cancer, or melanoma who are positive for CD73 expression centrally-assessed by immuno-histochemistry. To minimize physician/patient selection bias, patients will be randomized to either single agent LY3475070 (Cohort C2) or combination therapy of LY3475070 and pembrolizumab (Cohort C1).
- **Cohort D** will consist of men with metastatic castrate resistant prostate cancer; eligible patients must be naïve to PD-1/L1 therapy. To minimize physician/patient selection bias, patients will be randomized to either single agent LY3475070 (Cohort D2) or combination therapy of LY3475070 and pembrolizumab (Cohort D1).
- **Cohort E** will consist of patients with metastatic triple negative breast cancer who have received at least 1 line of systemic treatment for metastatic disease; prior PD-1/L1 inhibitor is allowed but not required. Patients will receive combination therapy of LY3475070 and pembrolizumab.

**Disclosure Statement:** This is a treatment study with dose escalation and dose expansion phases that has no blinding or masking.

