## **6.3. Measures to Minimize Bias: Randomization and Blinding**

This is an open-label dose finding study.

The Phase 1b dose expansion part will implement a randomization design for Cohorts C and D to mitigate the selection bias in allocating patients to either monotherapy dose expansion or combination therapy dose expansion.

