### 9.4.3.3. Tertiary/Exploratory Analyses

Overall survival (OS), as well as the efficacy parameters based on iRECIST will also be analyzed as the exploratory objectives. The definition of efficacy endpoints based on iRECIST will be described in the SAP.

**Overall survival** is defined as the time from the first start of study treatments until death from any cause. If the patient is alive, lost to follow-up, or withdrawn from study at the time of data analysis, OS data will be censored on the last date the patient is known to be alive.

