DLT evaluable	All patients enrolled in the dose escalation phase (Phase 1a) who either complete 28 days of follow-up and at least 75% of treatment doses or discontinue treatment prior to 28 days due to a DLT.
Randomized	(Phase 1b portion only). All patients in cohorts C and D who are randomized to a treatment regimen, regardless of whether they take any study drug.
PK evaluable	All enrolled patients who have at least 1 postbaseline evaluable PK sample.
Safety	All participants who take at least 1 dose of study treatment. Participants will be included in the treatment group corresponding to their initial dose of study treatment, even if it is not the treatment to which they were assigned. In the event of a treatment error, participants will be analyzed according to the treatment they actually received. “Enrolled” population also refers to the “Safety” population in this study.
Screen Failures	Patients who have signed informed consent, do not meet eligibility criteria and are not enrolled.

Abbreviations: DLT = dose-limiting toxicity; PK = pharmacokinetic(s).

Any change to the data analysis methods described in the protocol/SAP will require an amendment ONLY if it changes a principal feature of the protocol/SAP. Any other change to the data analysis methods described in the protocol/SAP, and the justification for making the change, will be described in the clinical study report. Additional exploratory analyses will be conducted as deemed appropriate.

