6.7. Efficacy Analyses

The antitumor activity of LY3475070 monotherapy and in combination with pembrolizumab will be assessed based on RECIST 1.1 and iRECIST (Seymour et al. 2017), respectively. The

efficacy analyses will be focused on treated participants (safety populations) in Phase 1a part of the study (dose escalation), and in Phase 1b part of the study (dose expansion).

The Kaplan-Meier method (Kaplan and Meier 1958) will be used to estimate the curves, median time and 95% CI of time to event parameters such as OS, PFS and DoR based on RECIST 1.1, iPFS and iDOR based on iRECIST for each arm of Cohorts C and D, and Cohort E. Overall response rate (ORR based on RECIST 1.1 and iORR based on iRECIST), with corresponding 95% exact CI, will be summarized for each arm of Cohorts C and D, and Cohort E. ORR with corresponding 95% exact CI will also be summarized for the monotherapy and combination cohorts in Phase 1a part of the study.

The following definitions for efficacy endpoints will be used:

Primary Endpoint

Overall response rate (ORR) is defined as the number of patients who achieve a best overall response of complete response (CR) or partial response (PR) divided by the total number of patients treated (safety population). The ORR, with 95% CI, will be summarized for each study part.

Secondary Endpoints

The **disease control rate (DCR)**, defined as the proportion of patients who achieved a CR or PR or stable disease (SD) out of all patients treated, will also be summarized. Best response is determined from a sequence of responses assessed. Two objective status determinations of CR before progression are required for a best response of CR. Two determinations of PR or better before progression, but not qualifying for a CR, are required for a best response of PR.

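### Section 7.3 commits to vital-status tracing only for randomized participants, which leaves out single-arm Cohort E although its overall survival is to be estimated

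*Protocol*

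**What the plan says.** **Tracing.** Protocol Section 7.3 has two layers. The first applies to every participant: "Site personnel are expected to make diligent attempts to contact participants who fail to return for a scheduled visit". The second is a search for vital status by site personnel or an independent third party, which may use public sources. It is to be attempted "within legal and ethical boundaries for all participants randomized, including those who did not get investigational product". Success changes the patient's status: "If vital status is determined, this will be documented and the participant will not be considered lost to follow-up".

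**Who is randomized.** Protocol Section 6.3: "The Phase 1b dose expansion part will implement a randomization design for Cohorts C and D". The Randomized set in SAP 6.1 has the same limit: "All patients in cohorts C and D who are randomized to a treatment regimen, regardless of whether they take any study drug". For Cohort E the Protocol synopsis (Overall Design) gives one regimen and no allocation step: "Patients will receive combination therapy of LY3475070 and pembrolizumab".

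**How OS is used.** Protocol Section 3 and SAP 4.2 list OS among the Phase 1b secondary endpoints, with no restriction by cohort. Protocol Section 9.4.3.3 places it with the exploratory analyses. SAP 6.7 plans Kaplan-Meier curves, medians and 95% confidence intervals for "OS, PFS and DoR based on RECIST 1.1, iPFS and iDOR based on iRECIST for each arm of Cohorts C and D, and Cohort E". For a patient who is alive, lost or withdrawn at the time of analysis, Section 9.4.3.3 states that "OS data will be censored on the last date the patient is known to be alive".

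**Routine follow-up.** The Schedule of Activities (Protocol Section 1.3) collects survival every 90 days in long-term follow-up and accepts telephone contact. Its footnote ends that follow-up at death, withdrawal or loss to follow-up.

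**The concern.** The patients covered by the tracing commitment are not the patients whose OS is estimated. Efficacy is analysed in treated patients (Protocol Section 9.4.1, SAP 6.7). The commitment reaches randomized patients who were never dosed, who are outside that set, and misses treated Cohort E patients, who are inside it. The wording would fit a trial in which every patient is randomized.

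This matters because the vital-status search is the step that remains once routine contact has failed. Without it, a Cohort E patient who drops out of contact is censored at the last date known alive, and Kaplan-Meier assumes that such patients go on to die at the same rate as those still observed. In advanced cancer, patients may go out of contact because they are deteriorating. If so, the censoring is informative and the Cohort E curve is too high. A single-arm estimate has no concurrent control group that would share the error.

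**Working it through.** **1. Patients outside the commitment.** From the Protocol synopsis (Number of Participants):
- Phase 1b total: Cohort C 50 + Cohort D 50 + Cohort E 40 = 140. This reproduces the stated maximum.
- Not randomized by the documents' own description: Cohort E, 40/140 = 28.6%.
- Phase 1a is also not randomized, but OS is not a Phase 1a endpoint.

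These are patients outside the clause, not patients affected. Only those who are lost are affected. At 5%, 10% or 20% loss that is at most 2, 4 or 8 of 40.

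**2. Size of the effect.** The documents give no loss rate, survival assumption or OS event count, so everything below is assumed. Take exponential survival with a 12-month median: hazard h = ln 2/12 = 0.05776 per month and true 12-month OS 0.50 for patients who stay in contact. The traced result assumes that every search succeeds. Section 7.3 promises only an attempt, so each figure is a ceiling for its scenario.

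*Scenario A: a share L of patients is lost at a time u, uniform over months 1 to 6 if still alive, and then has hazard r × h.*
- Untraced: the hazard among observed patients stays at h, so Kaplan-Meier gives exp(−12h) = 0.50 whatever L and r are.
- Traced: S(12) = (1 − L) × 0.50 + L × q, where q is the mean of exp(−hu − rh(12 − u)) over u.
- r = 1: q = 0.50.
- r = 2: q = 0.25 × 1.2283 = 0.307.
- r = 3: q = 0.125 × 1.5192 = 0.190.

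| L | Traced, r = 1 | Traced, r = 2 | Traced, r = 3 | Overstatement (0.50 minus traced) |
|---|---|---|---|---|
| 5% | 0.500 | 0.490 | 0.485 | 0 to 1.6 points |
| 10% | 0.500 | 0.481 | 0.469 | 0 to 3.1 points |
| 20% | 0.500 | 0.461 | 0.438 | 0 to 6.2 points |

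A simulation of the same set-up agrees to within about 0.001 to 0.002.

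*Scenario B: a share p of deaths is never found, and those patients were last seen 0 to 3 months (uniform) before death.* This is strongly informative by construction, because nobody is lost except shortly before dying.
- The observed hazard is a × h, with a = (1 − p)/[(1 − p) + p × k] and k = (1 − exp(−3h))/(3h) = 0.918.
- Untraced 12-month OS is 0.50^a, against a true 0.50. The apparent median is 12/a months, against 12.

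| p | a | Untraced 12-month OS | Overstatement | Apparent median (months) |
|---|---|---|---|---|
| 5% | 0.954 | 0.516 | 1.6 points | 12.6 |
| 10% | 0.907 | 0.533 | 3.3 points | 13.2 |
| 20% | 0.813 | 0.569 | 6.9 points | 14.8 |

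Simulation with N = 40 and 12 to 30 months of follow-up gives about the same: 0.53 at 10% and 0.57 at 20%.

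**3. Scale against sampling error.** With 40 patients the standard error of a 12-month OS of 0.50 is about √(0.5 × 0.5/40) = 0.079. The 10% cases (at most 3.3 points) are under half a standard error, and the worst 20% case (6.9 points) is a little under one. Unlike sampling error, this error goes in one direction whenever lost patients fare worse, and the confidence interval does not allow for it.

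**The case against.** **Existing follow-up already covers Cohort E.** This largely stands. Diligent contact attempts and 90-day survival contacts apply to all patients, so the gap opens only when these fail, and the number lost may be very small. But long-term follow-up ends at loss, and no passage found extends the search beyond randomized patients.

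**Nothing forbids tracing Cohort E.** True. Section 7.3 promises only an attempt for Cohorts C and D, so full tracing there against none in Cohort E would be too stark a reading. Still, a practice left to each site is not a commitment, and a site could reasonably decline a public-records search that the protocol does not call for.

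**The bias may be nil.** This stands. If loss is unrelated to prognosis, both the traced and untraced curves give 0.50.

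**OS carries little weight here.** No formal test of improvement is planned (Section 9.1), the Section 9.5 expansion decisions name no OS criterion, and OS is secondary in one place and exploratory in another. This limits how serious the point is.

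**Tracing randomized but undosed patients is not an error.** Agreed. The SAP defines a set that contains them, and tracing them does no harm.

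**A wider reading.** A reader might infer that up to 80 of 140 patients (57%) are outside the rule. Section 9.5 allows 20 more combination patients in each of Cohorts C and D, and 10 + 20 + 20 = 50 uses up each cap with no monotherapy places left. Those 40 patients may indeed fall outside the rule if they are not randomized. But the documents describe Cohorts C and D as randomized without exception and do not say how the added patients are assigned, so the larger figure is not established.

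**Conclusion.** The point holds for Cohort E: up to 40 of 140 Phase 1b patients (29%) have a planned OS estimate but no commitment to vital-status tracing. If 5% to 20% are lost, 12-month OS would be overstated by 0 percentage points with non-informative loss and by up to about 6 to 7 points with strongly informative loss at 20%. This assumes exponential survival with a 12-month median, the loss patterns set out above, and searches that always succeed. The actual loss rate is unknown.

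A reader might also infer that OS comparisons between Cohort E and the randomized cohorts, or between arms, would be biased. The documents do not support this. SAP 6.7 gives separate descriptive estimates by arm and cohort, Cohort E is a different tumor type, and no comparison between cohorts is planned. The risk is an optimistic OS estimate for Cohort E. That deserves correction because the correction is easy, but it does not threaten the primary objectives.

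**What to change.** In the Section 7.3 sentence on vital status, replace the reference to randomized participants, with its clause on those not given product, by: *all participants enrolled in Phase 1b (Cohorts C, D and E), and any participant randomized but not treated*. The second part is needed because Protocol Section 9.3 equates enrolled with having taken at least one dose. The wording also covers any post-interim patients in Cohorts C and D, however they are assigned.

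The same amendment could settle whether OS is secondary (Section 3, SAP 4.2) or exploratory (Section 9.4.3.3).

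The cost is one phrase in the next amendment and a small extra effort for the few patients lost, using the search process already in place. No treatment, endpoint or sample size changes.

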## 8. Study Assessments and Procedures

- Study procedures and their timing are summarized in the SoA (Section 1.3). Protocol waivers or exemptions are not allowed.
- Immediate safety concerns should be discussed with the sponsor immediately upon occurrence or awareness to determine if the participant should continue or discontinue study intervention.
- Adherence to the study design requirements, including those specified in the SoA (Section 1.3), is essential and required for study conduct.
- All screening evaluations must be completed and reviewed to confirm that potential participants meet all eligibility criteria. The investigator will maintain a screening log to record details of all participants screened and to confirm eligibility or record reasons for screening failure, as applicable.
- Procedures conducted as part of the participant's routine clinical management (e.g., blood count) and obtained before signing of the ICF may be utilized for screening or baseline purposes provided the procedures met the protocol-specified criteria and were performed within the time frame defined in the SoA (Section 1.3).

### 8.1. Efficacy Assessments

#### 8.1.1. RECIST V1.1 for Tumor Response Assessment

Please follow the guidelines below when assessing tumor response:

- Response Evaluation Criteria in Solid Tumors (RECIST) v1.1 will be applied as the primary criteria for assessment of tumor response (Eisenhauer et al. 2009).
- The extent of computed tomography (CT) or magnetic resonance imaging needed to establish baseline tumor burden is based upon the investigator's determination.
- Tumor assessments will be performed for each patient at the times shown in the SoA (Section 1.3). Counting from C1D1, for the first year of study treatment, disease status should be evaluated radiologically per RECIST v1.1 guidelines every 9 weeks ( $\pm 7$  days) for the first year, and every 12 weeks ( $\pm 7$  days) thereafter (until a discontinuation criterion is met).
- Perform assessments as scheduled, even if study treatment is delayed or omitted, except when deemed not feasible in the opinion of the investigator because of the patient's clinical status.
- Standard of care scan (pre-ICF) may be used as baseline provided it meets technical requirements for inclusion criteria and occurred within 28 days of treatment.

Per RECIST v1.1 imaging guidelines:

- imaging modality (e.g., CT or magnetic resonance imaging [MRI]) obtained for the study baseline should be repeated throughout the study as described in SoA;
- Intravenous and oral contrast should be used as clinically indicated;
- While CT imaging with slices  $\leq 5$  mm, MRI imaging is also acceptable;

- CT images from positron emission tomography-CT scans may be used for response assessment if the associated CT scan has the same quality as a diagnostic CT.

Best overall response (BOR; e.g., complete or partial response, stable disease or unknown) will be determined locally by the investigator per RECIST v1.1; there will be no independent review of BOR. When the RECIST v1.1 criteria for progressive disease are met, clinically stable patients may undergo additional radiologic imaging progression for confirmation of PD per iRECIST (Section 8.1.1, Seymour et al 2017). For patients who meet criteria to continue treatment after initial progression (either awaiting confirmation by iRECIST or have iUPD by iRECIST), reconsenting is required. Patients who discontinue treatment without documented progression should continue to be assessed for patients who discontinue study treatment without confirmed PD, periodic imaging per SoA (Section 1.3) for PD confirmation will continue until PD, or initiation of subsequent therapy or withdrawal of consent. If the patient is still on study treatment after 1 year, perform tumor imaging Q12W.

